2.0 Device Description

Device Description

The Mobility+ Enteral Feeding System (“Mobility+ System”) is a portable, lightweight, non-electronic, disposable enteral feeding system intended to deliver commercially available liquid nutrition formula to a patient, using a standard extension set (or feeding tube) with an ENFit® connector, in the clinical or home care settings.

The Mobility+ System delivers formula using a simple container system (“Feeding Pouch”) that has an internal elastomeric pump, filled by the user with formula, that gradually deflates once enabled. The deflation of the elastomeric pump generates a consistent, low pressure that gently pushes the formula from inside the elastomeric pump through the supplied tubing set (“Giving Set”) to the user’s extension set (or feeding tube), where the formula enters their digestive system through a surgically placed stoma. The progress of formula delivery is indicated by reductions in Feeding pouch inflation and weight, and completion of formula delivery is indicated by a cessation in formula flow out of the giving-set. Clinicians will consult product labelling to determine which giving-set patients should be guided to use, to provide for their individual flow rate needs. The system can be worn in a bag of choice, or in clothing, that can fit the system without kinking the tubing.

The Mobility+ System is self-contained, portable and does not require an external pump, power source, or IV pole. It is designed to provide the patient greater mobility and overall ease of use. It operates silently, avoiding noises which can prove distracting and sleep disrupting for patients requiring night-time feeding. It offers the overall simplicity of operation of gravity-fed systems without requiring gravity to deliver formula to the patient.

Figure 1: The Mobility+ System. Feeding Pouch (left), Filling Set and Giving Set (right);

The Mobility+ System is single patient use, disposable and intended for use over a 24-hour period. It has three primary components (Figure 1).

Primary components

The Feeding Pouch

The combined pump and reservoir of the Mobility+ System (Figure 2). It consists of a flexible protective sleeve with an internal silicone elastomeric pump.

To fill the Feeding Pouch, the Filling Set is attached to the spout. As the Feeding Pouch is filled with formula, it inflates. This inflation generates the mechanical force used to dispense the formula in a controlled manner, without any external energy source or need for gravity. Once filled, the Filling set is detached from the spout. The Feeding Pouch can hold a maximum of 500 ml of formula and a minimum of 250 ml.

[figure not shown]

Figure 2: Feeding Pouch (left), Internal Schematics (right, empty & full)

The Filling Set

Tubing that transfers commercially available nutritional formula from its packaging to the Feeding Pouch using ENFit® connectors and a syringe (Figure 3).

[figure not shown]

Figure 3: The Filling Set and Syringe

Note: A 60 ml ENFit® syringe (Figure 3) is not included with the Mobility+ System. It is an ancillary device used in the transfer of formula from the formula packaging ('feed container' in Figure 3) to the Feeding Pouch, with the use of the Filling Set.

The Giving Set

Tubing that connects the Feeding Pouch to the ENFit® connector of the user's extension set (or feeding tube), (Figure 4). The Giving Set is available in a variety of lengths to give a range of formula flow rates (Figure 5).

Once the Feeding pouch is filled using the Filling set (figure 3), the Giving Set is attached to the Feeding Pouch with the clamp of the Giving Set tubing closed. Formula flow is enabled by opening the clamp. The system is then primed (allowing the Feeding Pouch to fill the Giving Set tubing with formula to clear air, if any, from the elastomeric pump and the Giving Set tubing itself). The formula flow is disabled by closing the clamp. The Giving Set is attached to the extension set (or feeding tube). The Mobility+ System is now ready. Once again, formula flow is enabled by opening the clamp.

[figure not shown]

Figure 4: The Giving Set

[figure not shown]

Figure 5: Available Giving Set lengths

The Mobility+ System may be worn in a bag of choice that can fit the filled Feeding Pouch without kinking the Giving Set tubing. The Instructions for Use guides the user to place the spout of the Feeding Pouch within 15cm (6 inches) above or below the user's stoma when feeding. All connectors in the Mobility+ System comply with the FDA-recognized ENFit® standard (ISO 80369-3 and ISO 18250-3).

2.1 Intended Use and Indications for Use

Intended Use

The Rockfield Medical Devices Mobility+ Enteral Feeding System is intended to deliver liquid nutrition formula to an enteral access device (feeding tube) in users aged 2 years and over.

Indications for Use

The Rockfield Medical Devices Mobility+ Enteral Feeding System is intended to deliver liquid nutrition formula to an enteral access device (feeding tube) in users aged 2 years and over.

3.0 Purpose

The purpose is to evaluate the safety and effectiveness of Mobility+ enteral feeding system via this initial post-market study (510k clearance number K222678) in adults, a subset of the intended use population. This evaluation will be conducted in a prospective, single arm, non-randomized clinical study.

Hypothesis and Objectives

The study hypothesis is that Mobility+ meets its intended use, safely. The objectives are to evaluate the below primary and secondary endpoints, through execution of this protocol:

Endpoint	Detail	How it will be measured
Primary: Safety and Effectiveness of Mobility+	Evaluate participants who have received familiarization training can use device, according to IFU, to allow delivery of liquid nutrition to their feeding tube, in a real-life setting (home), safely (i.e. can execute critical device use tasks to allow feeding, without serious adverse events) and with effectiveness (i.e. using Mobility+ for the majority or all of their feeding sessions i.e. two daily feeds, minimum)	Phone communication and checklist (Appendix8)

Secondary: Usability of Mobility+	Evaluate Participant perspectives on mobility, ease of use and tolerance, with their current feeding system(s) and Mobility+	Participant perspectives surveys: Baseline (Appendix 4) End of study (Appendix 7)
	Evaluate changes in participant Quality of Life (QoL)	QoL survey at baseline (Appendix 5) and QoL question at end of study (Appendix 7)
	Estimate if participants consume similar average volume (and kcals) of feed/day during the study, compared to baseline	Collect descriptive data on estimated average feed volume and kcals consumed at baseline (Appendix 3) and at end of study (Appendix 8)

The outcome will be presented in a study report.

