7.0 Definitions

Term	Description
User	Person interaction with medical device
Operator	Operators are study staff who have self-trained in the use of Mobility+ and who have received training in the execution of this Protocol by the sponsor, Rockfield Medical Devices. Study staff in this study comprise advanced nursing practitioners, registered dietitians, researchers and principal investigator.
Participant	Individual who is or becomes a participant in a clinical investigation, as a recipient of the investigational device. Note that 'participants' in this study are users of the device who are being enterally fed in clinical settings or who are feeding at home (as per Usability Engineering File DR010).
Investigational medical device	Medical device being assessed for clinical performance, effectiveness, or safety in a clinical investigation
Clinical effectiveness	Achievement of a clinically significant intended result in a defined portion of the target population when the investigational medical device is used within its intended uses and according to its instructions for use, as determined by documented scientific evidence
Malfunction	Failure of an investigational medical device to perform in accordance with its intended purpose when used in accordance with the instructions for use
Principal Investigator	Qualified person responsible for conducting the clinical investigation at an investigation site
Use error (ISO 14155:2020)	User action or lack of action while using the medical device that leads to a different result than that intended by the manufacturer or expected by the user. Note: Use error includes inability of the user to complete a task.
Adverse event (AE) (ISO 14155:2020)	Untoward medical occurrence, unintended disease or injury, or untoward clinical signs (including abnormal laboratory findings) in subjects, users or other persons, whether or not related to the investigational medical device and whether anticipated or unanticipated
Serious adverse	adverse event that led to any of the following

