8.3 Participants

This is a first in human post-market clinical study to evaluate the Mobility+ system, being carried out following market approval (i.e., FDA clearance). 25 participants will be enrolled to ensure data can be obtained for 20 participants (the expected drop-out rate is estimated at ~20%), as this is considered appropriate for a post-market clinical study on a low-risk device and will add meaningful data to device risk management files. If more than 5 participants drop out, re-recruitment will aim to bring the sample size up to 20.

Recruitment will aim to obtain a mix of female and male participants who meet the inclusion criteria. Screening questions will be used by operators during the recruitment process to ensure participants are eligible (See **Appendix 1** and **Appendix 2**).

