5.0 Statistical test applied

The statistical test used was a paired T-test with ANOVA. Statistical significance was set at $P < 0.05$. Analyses were performed with IBM SPSS Statistics for Windows, version 29.0.1 (IBM Corp., Armonk, N.Y., USA).

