7.0 Supplemental Outcome data gathered

The following supplemental Outcome Data was gathered (n=17).

Compliance and Effectiveness (n (%))	
Successfully and safely feed with Mobility+	17 (100)
Achieved use of Mobility+ for minimum 2 daily EN feeds	16 (94.1)

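### The joint safety-and-effectiveness primary endpoint has no specified analysis; the SAP gives only two component percentages, without intervals, and the 100% is not the primary result

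*Protocol*

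**What the plan says.** **Endpoint and hypothesis.** Protocol 3.0 describes the design: "This evaluation will be conducted in a prospective, single arm, non-randomized clinical study". Its hypothesis reads: "The study hypothesis is that Mobility+ meets its intended use, safely". The primary endpoint is defined for the individual participant. The safety part is that the participant "can execute critical device use tasks to allow feeding, without serious adverse events". The effectiveness part is "using Mobility+ for the majority or all of their feeding sessions i.e. two daily feeds, minimum". The two parts are joined by an emphasised *and*, and the instrument is the Appendix 8 phone checklist.

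**Cohort-level criterion.** There is none. Protocol 7.0 defines clinical effectiveness as "Achievement of a clinically significant intended result in a defined portion of the target population", but that portion is not specified anywhere. Protocol 8.3 justifies the sample size by saying that "this is considered appropriate for a post-market clinical study on a low-risk device", with no power or precision figure.

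**Analysis.** Protocol Table 5 (11.2) has rows for the perspective surveys, quality of life and the end-of-study questions, and none for the primary endpoint. SAP 4.0 scores the rating items from 1 to 5. SAP 5.0 then states: "The statistical test used was a paired T-test with ANOVA". No other method is named.

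**Results shown.** SAP 7.0, on n=17, gives 17 (100) for feeding successfully and safely, and 16 (94.1) for "Achieved use of Mobility+ for minimum 2 daily EN feeds". SAP 3.0 gives 19 participants included.

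**The concern.** The endpoint that carries the study's safety and effectiveness question is the one measurement with no analysis written for it. A reader of SAP 7.0 meets 100% first, and nothing there says that it is one component, how precise it is, or which day it describes. Appendix 8 asks both items on Study Day 7 and again on Study Day 14.

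The 100% also rests on a single self-reported yes/no question. It is not a count of participants who completed the critical tasks without an SAE, and the SAP gives neither of those results.

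The denominator matters for safety in particular. Protocol 8.13 ends participation on any hospitalization, and Protocol 7.0 lists in-patient hospitalization among the SAE criteria. An analysis restricted to people with end-of-study data can therefore leave out those who had an SAE. Protocol 9.0 says that the risk-benefit files will be updated after the study report, so the figures will be used.

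**Working it through.** **1. Reproduce the plan's own figures.**
- Enrolment (Protocol 8.3: 20 with data, about 20% dropout): 20 / (1 − 0.20) = 25, as stated.
- Participant flow (SAP 3.0): 548 − 493 − 11 − 25 = 19, and 493/548 = 90.0%, as stated.
- Results (SAP 7.0): 17/17 = 100% and 16/17 = 94.1%, as stated.
- Included but not in the outcome table: 19 − 17 = 2. The SAP does not explain them.

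**2. Can the named test be used for the primary endpoint?** A paired t-test needs a within-person difference on a numeric scale. The two Appendix 8 items are yes/no and are asked only on Mobility+, so there is no baseline value to pair with. Pairing Day 7 with Day 14 would test change over time, not the endpoint, and a 17/17 item has zero variance. The test fits the before-after ratings of SAP 4.0 and cannot serve here.

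**3. Bound on the joint result.** Success requires both parts, so the joint count cannot exceed the smaller component: min(17, 16) = 16 of 17. It could be lower, since critical-task and SAE results are not reported.

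**4. Exact (Clopper-Pearson) 95% limits.** For x successes in n, the lower limit is the 0.025 quantile of Beta(x, n − x + 1) and the upper limit is the 0.975 quantile of Beta(x + 1, n − x). When x = n, the lower limit reduces to 0.025^(1/n), so for 17/17 it is 0.025^(1/17) = 0.805.

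| Item | Count | Estimate | Exact 95% limits |
|---|---|---|---|
| Successful and safe feeding, reported | 17/17 | 100% | 80.5% to 100% |
| Two daily feeds, reported (also the ceiling for the joint result) | 16/17 | 94.1% | 71.3% to 99.9% |
| Successful and safe feeding, two unreported counted as failures (assumption) | 17/19 | 89.5% | 66.9% to 98.7% |
| Two daily feeds, two unreported counted as failures (assumption) | 16/19 | 84.2% | 60.4% to 96.6% |

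Wilson limits are close: 81.6% to 100% for 17/17, and 73.0% to 99.0% for 16/17.

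**5. SAEs.** The SAP gives no count. If there were none (assumption), the exact two-sided 95% upper limit is 1 − 0.025^(1/n):
- n = 17: 19.5%
- n = 19: 17.6%
- n = 20, as planned: 16.8%

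For scale, an SAE affecting 1 user in 50 (an illustrative rate) would appear at least once among 17 people with probability 1 − 0.98^17 = 0.29.

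**The case against.** The best defence is that this is a small, single-arm, post-market study of a cleared device that the protocol calls low-risk. A descriptive proportion needs no test, the denominator of 17 is printed so anyone can derive an interval, and SAP 5.0 follows the rating scores and was most naturally meant for them. A participant-level criterion does exist in Protocol 3.0, and Protocol 8.6 adds that use below two daily feeds will be reported with sub-analyses.

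Much of that stands. The gap is an omitted primary analysis, not a test wrongly assigned to the endpoint. But a descriptive study with a stated hypothesis still has to report its primary endpoint as defined and show its precision. The joint result and the SAE count cannot be recovered from the printed table.

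Some stronger readings are tempting, but the documents do not support them:
- *The sponsor treats 100% as proof that the hypothesis holds.* Neither document draws that conclusion. The SAP lists counts, and the study report is not among the documents.
- *The primary result was demoted to supplemental.* SAP 1.0 and 6.0 use the same label for baseline data, and the two rows are components or proxies, not the endpoint itself.
- *Seventeen people are too few to support the hypothesis.* With no rate named, there is nothing to fall short of. What can be said is that the precision is unreported.
- *A failure at Day 7 was hidden by a success at Day 14, or the two unreported participants had SAEs.* Both are possible; neither is shown.

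**Conclusion.** The point holds as an omission with a measurable effect. The primary endpoint joins two parts, has no specified analysis, and is not reported. The joint result is at most 16/17 on the day or days that SAP 7.0 describes, so 100% is not the primary result.

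On the reported data, the ceiling of 94.1% carries a lower limit of 71.3%. If both unreported participants are counted as failures, the ceiling falls to 84.2% and its lower limit to 60.4%. That treatment of the two is an assumption, as is zero SAEs in the 19.5% and 17.6% upper limits. The exact limits for 17/17 and 16/17 rest only on the printed counts. Which day those counts refer to remains unknown.

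**What to change.** In the SAP and the study report:
- Present the participant-level joint endpoint and each component as the primary analysis, with exact (Clopper-Pearson) 95% limits, on the 17 with data and on all 19 included. Account for the two not reported.
- State the day for each figure and show Day 7 and Day 14 separately. A summary that requires success on both days may be added only as a sensitivity analysis labelled post hoc, because neither document defines it and results are already known.
- Report the SAE count with its exact upper limit among everyone who used the device, including anyone withdrawn for hospitalization.
- Say that the paired test in SAP 5.0 applies to the before-after ratings only.
- Word the conclusion as estimation, quoting the joint-endpoint interval. Set no success threshold now.

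The cost is some SAP and report wording and a few lines of calculation on data that the study planned to collect. The downside is a less favourable headline.

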Note: In considering functional capacity, the operator will consider the ability to conduct critical tasks associated with successful use of Mobility+ (i.e. removal of protective caps; connecting filling set to pouch in correct orientation; operating clamps; orientating 3-way valve; pushing syringes of feed into pouch; disconnecting tubing (filling and giving sets); connecting giving set to extension set or feeding tube; wearing Mobility+ and coiled tubing on the body; Sit, walk, and stand while wearing Mobility+)

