		

How strongly do you agree with the following statement? I would like to use the Mobility+ again.

Strongly Agree	Somewhat Agree	Neutral	Somewhat Disagree	Strongly Disagree
				

If you would like to use Mobility+ again, how often would you like to use it?

Every Day	Every Week	Every Month
		

Think about your overall wellbeing if you used Mobility+ for SOME/ALL of your tube feeding needs, in the long term. How would your wellbeing be then, compared to now?

Much Better	Somewhat Better	About the Same	Somewhat Worse	Much Worse
				

Would you pay out of pocket for the Mobility+?

YES	NO
	

How did you choose to wear the Mobility+ system?

- Crossbody bag**
- Handbag**
- Backpack**
- In clothing**
- Clipped onto belt/clothing**
- Other (Detail):**

Appendix 8

Appendix 8 - Phone communication check sheet (Study Day 7 and 14) - (Operator asks the Participant these questions)

Day 7

Day 7			
Questions:	Answers:		
Day 7 Safety & Effectiveness Check			
Are you able to use Mobility+ to successfully and safely provide enteral feeding?	 YES  NO		
Day 7 Compliance & Calorie Intake Check			
Consider your feed intake over the last 3 days (i.e. Study day 4, 5, 6).			
Questions:	Answers:		
What volume of enteral nutrition did you consume on average per day (i.e. over 24 hr)?	Volume Mobility+mls		
How many hours did you typically infuse for, on average/day? hours minutes		
How many feedings did you intend to take using Mobility+ , on average / day?feedings		
How many feedings were you able to take using Mobility+ , on average / day?feedings		
What was the average volume of enteral nutrition that you consumed per feeding with Mobility+?mls		
What time of the day did you provide feedings with Mobility+?	Morning  Afternoon  Evening  Night-time 		
Operator facing question: On average, did the participant take at least two daily feeds with Mobility+? If no, why not?	 YES		
	 NO		
Day 7 Tubing SKU check			
Study Day 7:			
SKU that participant is using:			

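### The primary endpoint requires use according to the IFU with critical tasks executed, but its only named instrument, Appendix 8, records a self-rated yes/no and intake, with no item on any task, IFU condition or use error

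*Protocol*

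**What the plan says.** Protocol 3.0 sets the primary endpoint: participants who have had familiarization training "can use device, according to IFU, to allow delivery of liquid nutrition to their feeding tube, in a real-life setting (home), safely". It explains the safety part as meaning that they "can execute critical device use tasks to allow feeding, without serious adverse events", and the effectiveness part as using the device for most or all feeding sessions, with two feeds a day as the floor. The measurement column names one instrument, the phone checklist in Appendix 8.

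In Appendix 8, on Study Day 7 and again on Study Day 14, the operator asks the participant: "Are you able to use Mobility+ to successfully and safely provide enteral feeding"? The answer is yes or no. The remaining items are daily volume, infusion time, feeds intended and feeds taken, volume per feed, time of day, an operator yes/no on two daily feeds (with a reason if not met), and the tubing SKU.

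The only list of critical tasks in the visible text is the note to Protocol 8.4. There, an operator judging functional capacity at screening considers "the ability to conduct critical tasks associated with successful use of Mobility"+. The endpoint row does not refer to this list.

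Protocol 7.0 describes clinical effectiveness as a result obtained when the device is "used within its intended uses and according to its instructions for use, as determined by documented scientific evidence", and notes that "Use error includes inability of the user to complete a task". SAP 7.0 reports 17 (100%) feeding successfully and safely and 16 (94.1%) reaching two daily feeds, both with n = 17.

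**The concern.** The endpoint describes how the device is used; the instrument asks whether the participant feels able to feed. A participant who fed only with help, who recovered from a use error, or who fed with the spout outside the 15 cm range described in Protocol 2.0 can truthfully answer yes. Following the plan exactly therefore gives a result that does not measure the endpoint as written.

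Two uses of the result suffer. First, the conclusion that trained people can use the device at home according to the IFU has no direct record behind it. Second, Protocol 8.3 and 9.0 intend the study to feed the risk management files, including the FMEA. A global yes cannot show which step caused trouble. Nor can it help separate a use error from a malfunction, which Protocol 7.0 defines as "Failure of an investigational medical device to perform in accordance with its intended purpose when used in accordance with the instructions for use".

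**Working it through.** **The SAP's own figures.** 17/17 = 100% and 16/17 = 94.1%. Both reproduce.

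**Endpoint components against the forms.**

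| Component (Protocol 3.0) | On Appendix 8? | Elsewhere? |
|---|---|---|
| Use according to IFU | No item; volume per feed allows a rough comparison with the 250 ml minimum fill | Training covers the IFU (Appendix 11); no record of home adherence |
| Critical tasks executed | No task item; one global yes/no per call | Two of nine touched in Appendix 7 |
| No serious adverse event | No item | Recorded by the PI (Protocol 8.13 and 10.0, Appendices 9 and 10); admission question in Appendix 7 |
| At least two daily feeds | Yes, directly | – |

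**Task count.** The 8.4 note has nine entries: (1) protective caps, (2) filling-set connection, (3) clamps, (4) 3-way valve, (5) syringe filling, (6) disconnecting tubing, (7) giving-set connection, (8) wearing, (9) sitting, walking and standing with the device on.
- With their own item on Appendix 8: 0 of 9.
- Touched on Appendix 7: 2 of 9. It asks how the device was worn and how easy it was to move about.
- With no item on any visible form: 9 − 2 = 7. Appendix 12 records that the participant had the chance to carry out the steps in training, not that each step was carried out.

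**What delivered feed shows.** Protocol 2.0 describes a chain: fill through the filling set, detach it, attach and prime the giving set, connect, open the clamp. If formula arrived, someone completed the steps up to delivery. If the 17 yes answers are taken to mean that feed was delivered, there were 0 failures of the whole chain in 17. That is indirect evidence on most of the seven tasks without an item. It does not show who performed a step, whether an error came first, or whether conditions such as spout height were met.

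**Ceiling on the composite.** Success needs every component, and 16 of the 17 met the two-feeds criterion. So the composite is at most 16/17 = 94.1% (two-sided 95% Clopper-Pearson interval for 16/17: 71.3% to 99.9%). The 17/17 line (80.5% to 100%) belongs to the yes/no item alone.

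**What task lines would allow.** With 0 failures in n, the one-sided 95% upper bound on a task's failure rate is 1 − 0.05^(1/n):
- n = 17: 1 − 0.05^(1/17) = 16.2%
- n = 20 (the planned minimum): 13.9%
- n = 25 (the planned enrolment): 11.3%

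The sample size does not change.

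**The case against.** The strongest reply is that the endpoint concerns tasks needed to allow feeding, and feeding itself is recorded. If formula reached the participant, the delivery steps were done. This stands in part: a reader might infer that the study says nothing about task completion, and that goes too far. What is missing is who performed each step, whether errors occurred, and IFU conditions.

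A second reply is that a rule counting help or a prior error as failure would be a new endpoint. This stands. Protocol 3.0 says only that participants can execute the tasks, and it does not cite the 8.4 list. Wearing and moving about are not clearly needed for feeding.

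Third, problems have other routes: calls on Trial Days 1, 3 and 5, an operator phone number, PI recording of adverse events and device deficiencies, and the ease-of-use rating in Appendix 7. These cover the serious adverse event part of the endpoint. None has a field for use error or task performance, and the Appendix 8 reason field opens only when two feeds are missed. Figure 7, the IFU and the Usability Engineering File are not visible and may cover more.

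Fourth, Protocol 7.0 holds general definitions, Protocol 4.0 applies ISO 14155 only in part, and the SAP line nearly repeats the Appendix 8 wording under supplemental outcome data. That is fair. A reader might infer that the SAP claims verified IFU use; it does not.

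**Conclusion.** The mismatch is real. The primary endpoint names IFU use and critical task execution, and its single named instrument has an item for neither: 0 of 9 listed tasks on Appendix 8, and 7 of 9 with no item on any visible form. The SAP's 17/17 supports self-rated ability to feed. The composite including two daily feeds cannot exceed 16/17 (94.1%).

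This rests on reading the 8.4 note as the meaning of critical tasks, since it is the only such list in the visible text, and on the visible forms being the full set.

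A reader might go on to infer that the endpoint rate falls from 100% to some lower figure once hidden task failures are counted. The documents do not support this. They give no failure rate, the composite does not start from 100%, and a task failure in the one participant who missed two daily feeds would not change it.

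**What to change.** Under the Safety & Effectiveness Check in Appendix 8, on both calls, list the nine tasks from Protocol 8.4 with three boxes: done unaided, done with help or after an error, not able. Cite that list in the endpoint row. Count only the not-able answer as failing the can-execute component, and report help and errors per task descriptively, with exact confidence limits. If self-report of feeding is all that is wanted, instead reword the endpoint as self-reported ability to feed and remove the references to the IFU and critical tasks.

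For the data already collected, label 17/17 as self-rated ability to feed, report that the composite with two daily feeds is at most 16/17 (94.1%), and state that task execution and IFU conditions were not recorded.

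The cost is nine tick lines on each of two calls already scheduled, with no extra visit or participant. The calls become slightly longer. The answers remain self-report, so they locate difficulties by step but do not verify them. For the completed study the cost is a relabelled line and a short limitation statement.
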